Following the explanation, patients have their intake with a physical therapist. The patients able to perform training, will be prescribed a personalized exercise program and will be followed by a local physical therapist. This includes a training scheme for exercises at home (Appendix 2). They will be asked to train at home and once a week at the physical therapist, check their vital sings with the pulse oximeter and de SMM, and communicate these vital

Version number: 4

signs with the Luscii app to a call center Altide. In case of previously set limitations, this call center will contact the hospital (Appendix 3).

Home-monitored training

All eligible patients will participate in a three-to-nine-week (average of six weeks), partly supervised, home-monitored training program prior to elective AAA-repair. The second CPET measurement is planned after the training program. Training frequency during the prehabilitation will be five sessions per week including a weekly evaluation by the physical therapist. Training sessions at home are prepared and should be able to be performed without extra adjuncts (see below). Before and after home-monitored training sessions without a physical therapist, subjects communicate oxygen saturation, heartrate, blood pressure, number of steps (nS), and number of smoked cigarettes through the Luscii app. According to these measurements, automatic advises will be given through the app (Appendix 3).

To evaluate a difference after the average of six weeks, subjects visit the specialist in sports medicine a second time to perform a CPET. Depending on the performance of patients in relation to the improvement in this second CPET, a subdivision of an improved and a stable (not improved) group will be made. It is expected that improved patients will show an increase of their VO2 at VAT of 1,5 ml/kg/min or more.

Three months after surgery, monitoring is complete, and preoperative patient characteristics of the groups will be compared.

Home-monitored exercises

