Appendix 2; Exercise scheme at home and with the physical therapist

Maandag	Dinsdag	Woensdag	Donderdag	Vrijdag
20 minuten	20 minuten	Fysiotherapeut	20 minuten	20 minuten
wandelen	fietsen		wandelen	fietsen
2 minuten	2 minuten	Steep ramp test	2 minuten	2 minuten
traplopen	traplopen		traplopen	traplopen
1 minuut	1 minuut	HIIT	1 minuut	1 minuut
opstaan-zitten-	opstaan-zitten-		opstaan-zitten-	opstaan-zitten-
opstaan	opstaan		opstaan	opstaan

Table: example of a weekly training program

Thuis (4x per week): vaste tijd (bvb. 9u – 10u) overeengekomen met de fysiotherapeut.
Van tevoren zuurstofsaturatie, pols, RR en aantal sigaretten via de Luscii app
Op basis van CPET:

- 10 / 20 / 30 minuten per dag matig-intensief actief zijn (thuis, mensen merken dat ze meer moet ademhalen):
 - Wandelen
 - o Fietsen
- 1 / 2 / 5 minuten hoog-intensief (thuis):
 - Traplopen
 - o Opstaan uit de stoel en weer gaan zitten.

Na de training wederom O2, pols, RR via de Luscii app doorsturen.

Één keer per week fysiotherapie

[figure not shown]
Van tevoren zuurstofsaturatie, pols, RR en aantal sigaretten via de Luscii app Op basis van aangepaste steep ramp test (10 W /10 s):

Nadat de aangepaste SRT op baseline is uitgevoerd (Figuur 1, Grafieken A en C), kan het (gedeeltelijk) gesuperviseerde trainingsprogramma, bestaande uit 3 HIIT-sessies van 25 minuten per week, worden uitgevoerd in de leefomgeving van de patiënt (in de eerste lijn of thuis).

- Elke trainingssessie bestaat uit een warming-up van 3 minuten op een belasting van 20 W, gevolgd door 14 arbeidsintervallen van 30 seconden op een hoge intensiteit van 60% van de SRT Wpiek
- Afgewisseld met 14 herstelintervallen van 60 sec op een lage intensiteit van 20 W

 Waarna een cooling-down van 1 minuut volgt op een belasting van 20 W (Figuur 1, grafieken B en C).

De trainingsintensiteit tijdens de arbeidsintervallen met hoge intensiteit komt overeen met ongeveer 90% van de CPET Wpiek. De aangepaste SRT dient wekelijks of tweewekelijks herhaalt te worden om veranderingen in de cardiorespiratoire fitheid te monitoren, terwijl het programma dienovereenkomstig kan worden aangepast om een adequate trainingsprikkel te behouden.

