Appendix 3; Automatized answers Luscii.

Pulsoximeter		
Eerste meting (voor de training)	Zuurstofsaturatie 95 of lager	even rustig zitten, haal een paar keer diep adem en meet je zuurstofgehalte over een kwartier nog een keer. Je vindt de meting Zuurstofgehalte voor de training bij Zelfzorg onder het kopje Metingen. Zorg ervoor dat je handen warm zijn en haal eventuele nagellak of gelnagels weg. Blijft je zuurstofgehalte lager dan 95%? Overleg dan met je fysiotherapeut of je mag gaan trainen.
Eerste meting (voor de training)	Zuurstofsaturatie 95,1 of hoger	Je zuurstofgehalte is goed, je kan starten met je training. Vergeet niet om na de training je metingen in te vullen!
Tweede meting (na de training)	Zuurstofsaturatie 90 of lager	Je zuurstofgehalte is aan de lage kant. Train morgen iets minder hard en bespreek dit advies met je fysiotherapeut.
Tweede meting (na de training)	Zuurstofsaturatie 90 of hoger	Goed gewerkt, volgende keer weer een stukje beter. Gefeliciteerd!
Pols		
Eerste meting (voor de training)	Hartslag 70 of lager	Je hartslag is wat laag. Doe een lichte warming-up en bespreek dit advies met je fysiotherapeut. Meet na de warming-up nog een keer je hartslag. Je vindt de meting Hartslag voor de training bij Zelfzorg onder het kopje Metingen. Blijft je hartslag lager dan 70? Overleg dan met je fysiotherapeut of je door mag gaan met trainen.
Eerste meting (voor de training)	Hartslag 120 of hoger	Je hartslag is wat snel. Ga even rustig zitten en meet je hartslag over een kwartier nog een keer. Bespreek deze meting met de fysiotherapeut.
Tweede meting (na de training)	Hartslag 100 of hoger	Je hartslag is op dit moment wat hoog. Train morgen iets minder hard en bespreek dit advies met je fysiotherapeut.
Derde meting (30 seconden na de training)	Hartslag 120 of hoger	Kan een foute meting zijn. Als het morgen weer zo is, even met de fysiotherapeut bespreken, alstublieft.
Bloeddruk		
Eerste meting (voor de training)	Bovendruk 200mmHg of hoger	Ga niet trainen, meld deze meting volgende keer bij de fysiotherapeut
Eerste meting (voor de training)	Bovendruk onder de 200mmHg	U kan starten met trainen.
Tweede meting (na de training)	Bovendruk 200mmHg of hoger	Stop met trainen, meld deze meting volgende keer bij de fysiotherapeut
Tweede meting (na de training)	Bovendruk onder de 200mmHg	Goed gewerkt, volgende keer weer een stukje beter. Gefeliciteerd!
Stappenteller	 	1

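### The app's pre-training blood pressure rule in Appendix 3 has no lower end, so a low systolic reading is answered with a message that training may start, and no low-pressure limit is stated elsewhere

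*Protocol*

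**What the plan says.** Appendix 2 has the patient send readings before each home session: "Van tevoren zuurstofsaturatie, pols, RR en aantal sigaretten via de Luscii app". Section 3.1 likewise places the heart rate, blood pressure and saturation measurements before home training. Section 1 (Home-monitored training) links those readings to the app's replies: "According to these measurements, automatic advises will be given through the app (Appendix 3". For escalation by staff, Section 1 says "In case of previously set limitations, this call center will contact the hospital (Appendix 3", which points to the same appendix.

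The blood pressure part of Appendix 3 has two rows for the measurement before training. At 200 mmHg or more the patient is told not to train and to report the value to the physiotherapist next time. The other row is labelled "Bovendruk onder de 200mmHg" (systolic under 200 mmHg) and its reply is "U kan starten met trainen". After training there is the same split at 200, and every value below it earns congratulations.

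Low values of the other two vital signs are treated differently. For saturation of 95 or lower, the patient sits, re-measures and is then told "Blijft je zuurstofgehalte lager dan 95%? Overleg dan met je fysiotherapeut of je mag gaan trainen", that is, to ask before training. For a pulse of 70 or lower, the patient does a light warm-up, re-measures and is told "Blijft je hartslag lager dan 70? Overleg dan met je fysiotherapeut of je door mag gaan met trainen", that is, to ask whether to continue.

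**The concern.** The two pressure rows leave no value unanswered. A low reading therefore gets a positive instruction to begin, which is worse than getting no message. The home programme includes high-intensity stair-climbing and sit-to-stand work, done on four of the five weekly sessions without a physiotherapist present. The Summary and Section 11.2 both rely on monitoring to keep risk low, and Section 7.5 provides no safety board. The automatic reply is what the patient sees when deciding whether to start. If it clears a pressure that a clinician would want checked, the monitoring fails to hold that session. The stake is participant safety only; the primary comparison, the sample size and the analysis are untouched.

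**Working it through.** The protocol gives no figure to reproduce here, so the check is a reading of the rules.

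**1. Coverage of the pressure rule before training.** Systolic 200 or more: do not train. Systolic below 200: start. The two rows cover every possible value, so every low reading falls in the start row.

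**2. Low-side handling of the three pre-training vital signs (Appendix 3).**

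| Vital sign | Low-side trigger | Reply |
|---|---|---|
| Saturation | 95 or lower | Hold: sit, re-measure, ask before training |
| Pulse | 70 or lower | Caution: light warm-up, re-measure, ask whether to continue |
| Systolic pressure | none | Start |

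One of the three has a true hold, one has a caution given once light activity has begun, and blood pressure has neither.

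**3. Readings that pass every stated rule.** The saturation row "Zuurstofsaturatie 95,1 of hoger" (95.1 or higher) also gives a start message. Pulse has rows at 70 or lower and at 120 or higher, and none for 71 to 119. The table below traces an assumed systolic pressure of 80 mmHg; this value is for illustration and is not in the protocol.

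| Saturation | Pulse | Start messages | Hold or caution messages |
|---|---|---|---|
| 97 | 90 | 2 (pressure, saturation) | 0 |
| 94 | 90 | 1 (pressure) | 1 (saturation) |
| 97 | 65 | 2 (pressure, saturation) | 1 (pulse) |
| 97 | 125 | 2 (pressure, saturation) | 1 (pulse) |

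Only the first pattern, saturation 95.1 or higher with pulse 71 to 119, passes with nothing to slow the patient. In the other three the patient gets conflicting messages, because the pressure row still says start. Any systolic value below 200 gives the same counts, so the result does not depend on the choice of 80.

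**4. Is a lower limit stated anywhere else?**
- Section 1 refers the call centre's limits to Appendix 3, which has no low-pressure row.
- Section 6.3 has the hospital contacted about abnormal readings but does not define them.
- Section 11.1, item e, names only a rise in blood pressure as a possible side effect.
- Section 11.1, item j, has the treating physician contacted on deterioration, without a figure.
- The exclusion criteria (2.3), withdrawal (6.4), termination rules (6.7), safety section (7) and Appendices 1 and 2 contain no blood pressure limit.

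The number of low-pressure limits in the protocol is zero.

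**The case against.** The strongest reply is that Appendix 3 is a list of messages to patients and need not be the whole escalation scheme. No row in it says that the hospital is called, yet Sections 1 and 6.3 say that it will be, and Table 2 budgets a separate per-patient alert item. A staff alert layer therefore appears to exist, and its settings may include a low-pressure limit. Other safeguards also apply:
- clearance by cardiology and sports medicine, with a cardiopulmonary exercise test, before training (Summary, Sections 1 and 2.2);
- training in office hours only (Summary);
- contact with the communication centre before home training (Section 6.3), although the text does not say that the centre reads each pressure value;
- weekly physiotherapist review (Section 1);
- contact with the treating physician on deterioration (Section 11.1, item j).

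A rule on the high side only also matches the one blood pressure effect that the protocol names.

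Most of this stands as mitigation. It rules out a stronger conclusion that a reader might draw, namely that a hypotensive patient would train with no protection; the documents do not show that. A reader might also infer that low pulse is handled as firmly as low saturation. It is not, because the pulse row begins with a warm-up. The stated gap remains: none of these safeguards gives a pressure limit or alters the automatic message, and the one cross-reference for call-centre limits leads back to Appendix 3.

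**Conclusion.** The point holds as a defect in a stated rule. Followed exactly, Appendix 3 clears any low systolic reading, and nothing else in the protocol sets a limit. The residual gap is a low pressure together with saturation of 95.1 or higher and pulse 71 to 119, for which no stated rule produces a hold or caution. The conclusion rests on the printed rules alone; call-centre settings outside the protocol are not visible. The protocol gives neither a low-pressure threshold nor a rate of low readings, so the number of sessions wrongly cleared cannot be estimated. The change should be made, as a partly mitigated safety gap with an inexpensive remedy.

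**What to change.** **Before training.** Give the under-200 row a lower systolic limit chosen by the responsible clinicians. Below it, the app should tell the patient not to start, to rest and re-measure, and to contact the physiotherapist or hospital if the value stays low.

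**After training.** Give low readings their own message in place of congratulations: sit or lie down, re-measure, and call the physiotherapist or hospital if the value stays low or there are symptoms. The pre-training wording cannot be reused, since telling a patient not to start makes no sense once the session is over.

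If the call centre already works to a low-pressure limit, write it into Appendix 3 and align the app message with it.

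**Cost.** A text change in Appendix 3, a rule change in the app configuration, and a few held sessions or extra calls. Nothing changes in the endpoint, sample size or analysis.
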